1.0 Objectives / Specific Aims

Alcohol use is prevalent and problematic among youth, who are more likely than adults to initiate alcohol use, develop alcohol use disorder (AUD), and suffer lasting adverse alcohol-related consequences^{1,2}. Despite the clear need for youth-targeted AUD treatments, established psychosocial and behavioral interventions offer limited efficacy, with very few youth achieving sustained alcohol abstinence or reduction³. Pharmacotherapies play a key role in bolstering substance use disorder treatment outcomes in adults, but to date, no medications for AUD in youth have merited FDA approval. The development of safe and effective adjunctive medications to treat adolescent AUD is needed to improve treatment outcomes and to potentially reduce the long-term consequences of adolescent use.

Cannabidiol (CBD), one of the main phytocannabinoids in the *Cannabis sativa* plant⁴, is a potentially promising candidate pharmacotherapy for youth AUD. It is particularly appealing as a youth treatment option since it is non-intoxicating^{4,5}, appears generally well-tolerated, and demonstrates no signal of abuse liability⁶. Further, young people tend to have a more positive attitude towards natural or alternative medicine^{7,8}. CBD has many potential targets within the central nervous system that may mitigate the symptoms of AUD^{9,10} via modulation of the glutamatergic, GABAergic (gamma aminobutyric acid), dopaminergic, opioidergic, and endocannabinoid pathways¹¹⁻¹⁴. Preclinical work has shown that CBD affects an array of drinking behaviors (e.g., reduces ethanol seeking and intake; mitigates symptoms of withdrawal, relapse, anxiety, and impulsivity)^{9,10,15}, and recent clinical work has indicated CBD's potential to reduce alcohol intake within adults who endorse alcohol and cannabis co-use¹⁶. CBD's safety profile, potential mechanistic targets, and preliminary effects on alcohol-related behaviors in humans warrants research to assess the neural mechanisms and acute effects of CBD among youth with AUD.

Translational medication screening studies have the potential to rigorously evaluate the acute effects of promising compounds, such as CBD, for neural and behavioral target engagement prior to initiating large-scale efficacy trials. Magnetic resonance spectroscopy (MRS) and functional MRI (fMRI) are two translational, developmentally appropriate techniques that can be used in humans to assess the neural mechanisms of pharmacotherapies^{17,18}. MRS measures metabolite levels in the brain that are neural treatment targets (e.g., glutamate, GABA) and fMRI localizes and quantifies brain activity. Utilizing these neuroimaging methods will allow for investigation into the neural effects of CBD on two important aspects of AUD: modulation of 1) *in vivo* glutamate and GABA levels, two neurotransmitter systems involved in addictive behaviors¹⁹⁻²¹ that have been proposed as therapeutic targets of CBD^{13,14,22}, and 2) brain reactivity to alcohol cues, which can be reliably measured with fMRI in heavy drinking youth²³ and correlates with alcohol craving²⁴. Establishing the acute neurometabolic and neurobehavioral effects of CBD in youth with AUD will be a critical first step in the pharmacotherapy development pipeline before initiating larger scale trials.

Consistent with the trans-NIH initiative to identify neurally-informed novel substance use treatments for youth, the goal of this application is to test CBD as a potentially effective candidate medication for youth with AUD by leveraging developmentally informed neuroimaging methods (MRS, fMRI) and lab-based paradigm procedures. To accomplish this goal, this study will use a randomized, double-blind, within-subjects crossover design. In counterbalanced order, 50 youth (ages 16-22) who meet criteria for AUD (≥ 2 symptoms) will receive 600mg of CBD²⁵⁻³⁰ or placebo with a standardized snack (to modulate CBD absorption rates) three hours before a neuroimaging and behavioral assessment paradigm, separated by an approximate 18-day washout period³¹.

Aim 1: Quantify neurometabolic effects of CBD using MRS in youth with AUD: Youth with AUD will show increased levels of glutamate and GABA in the anterior cingulate after taking CBD compared to placebo.

Aim 2: Quantify neurobehavioral effects of CBD using fMRI alcohol cue reactivity in youth with AUD: Youth with AUD will show decreased cue reactivity in reward-related neural regions after taking CBD compared to placebo.

Aim 3: Examine psychophysiological effects of CBD during alcohol cues: *In vivo* response to olfactory alcohol cues (measured via heart rate, skin conductance, and subjective ratings) will be lower post CBD vs. placebo.

Adolescence and young adulthood are critical periods of time for intervention and treatment for emerging alcohol-related problems, and pharmacotherapies can provide significant support to evidence-based psychosocial interventions. In this proposal, we will leverage neuroimaging and behavioral data to examine the acute neurometabolic, neurobehavioral, and psychophysiological effects of CBD on youth with AUD to assess CBD's promise as a potential adjunctive medication for youth AUD. Findings will bridge a critical translational gap ("the valley of death"³²) in pharmacotherapy development for youth AUD, advancing methodology for rigorous neural-behavioral early efficacy testing of CBD. Effects established through this study could pave the way to a larger-scale clinical trial and, ultimately, improved long-term outcomes for young people suffering from AUD.

2.0 Background

SIGNIFICANCE

Alcohol use during adolescence and emerging adulthood is problematic and has long-term consequences. Alcohol is the most used substance among young people; 55% of 12th graders³³ and 72% of 18-25 year olds³⁴ endorsed past year alcohol use. Youth alcohol use is related to serious psychosocial problems, including comorbid psychopathology³⁵⁻³⁹, poorer academic success⁴⁰, and detrimental neurocognitive consequences^{41,42}. Further, early alcohol initiation increases the risk of subsequent alcohol use disorder (AUD) and related problems^{1,2,43}. Nearly 15% of youth meet the diagnostic criteria for AUD by age 18⁴⁴, and alarmingly, half of individuals that meet the criteria for lifetime AUD do so by the age of 21⁴⁵.

Existing youth substance use treatments are inadequate. Effective treatments during adolescence and young adulthood are critical for improving long-term outcomes. Current treatments for youth AUD are primarily psychosocial, such as cognitive behavioral therapy, family-based therapy, and motivational interviewing³. Psychosocial interventions have shown small to medium effects on reducing substance use during adolescence^{46,47}, and up to half of youth return to substance use within 12 months following treatment⁴⁸⁻⁵⁰. Given the modest efficacy of current psychosocial treatments, pharmacotherapy has been explored as a potential complement to the standard of care to improve outcomes⁵¹. However, there are limited data regarding the efficacy of pharmacotherapy in treating youth AUD, and the safety and efficacy of adult AUD medications cannot be extrapolated to youth⁵². This calls for the evaluation of treatments specifically for youth with AUD to improve treatment outcomes and to potentially reduce the long-term consequences of youth use. Natural or alternative medicine options may be particularly appealing for youth^{7,8}.

Cannabidiol (CBD) may be a promising pharmacotherapy for youth AUD. CBD is a non-intoxicating constituent of the *Cannabis sativa* plant that has garnered attention as an alternative therapy because of its wide range of therapeutic properties, including its effects on addictive behaviors⁵³. Specifically, there is a growing preclinical literature⁹ indicating that CBD reduces: alcohol consumption and motivation to drink⁵⁴⁻⁵⁷; alcohol relapse and withdrawal^{55,58}; and alcohol-related neurotoxicity^{59,60}. A study of adult alcohol and cannabis co-users found that high CBD cannabis (23% CBD, 1% THC) was related to a decrease in alcohol consumption over 5 days which was not seen in the THC (24% THC, 1% CBD) or THC plus CBD (9% THC, 10% CBD) groups¹⁶.

CBD's effects on alcohol consumption and AUD symptoms may be due to its multiple brain targets that overlap with systems underlying AUD. Inside the endocannabinoid system (ECS), CBD can act as an inverse agonist or negative allosteric modulator of cannabinoid receptors (CB1, CB2)^{12,61-63} and can change ECS signaling through inhibiting the enzymatic breakdown of anandamide (endogenous cannabinoid ligand)^{64,65}. CB1 and CB2 receptors are expressed throughout the mesocorticolimbic pathway, which is highly implicated in addictive behaviors (e.g., reward, decision-making, substance intake, motivation, withdrawal, and relapse)⁶⁶⁻⁶⁹. Thus, CBD may exert its effects on AUD symptoms through indirect modulation of the ECS. Outside of the ECS, CBD has been shown to modulate glutamate^{13,22}, gamma aminobutyric acid (GABA)¹⁴, dopamine⁷⁰, serotonin^{71,72}, and opioid⁷³ neurotransmission, all of which are crucial systems implicated in AUD and have each been proposed as treatment targets for adult AUD¹⁵. While it is harder to assess neural mechanisms in humans, CBD has been shown to increase glutamate levels in individuals with psychosis²⁵ and autism spectrum disorder²⁶ through specialized

neuroimaging techniques (discussed more below). Overall, CBD's mechanism of action makes it a promising potential candidate medication for youth with AUD.

In addition to the preliminary behavioral and mechanistic data, CBD has a record of general safety and tolerability^{6,74} with limited adverse events⁷⁵ or abuse liability^{6,76,77}. Due to the lack of data in humans, which is even more pronounced in youth, it is important to rigorously test the acute neural and alcohol-related behavioral effects of CBD as a candidate medication for youth AUD before moving forward with large scale clinical trials.

Lab-based paradigms can provide a critically important intermediary step in medication development, from preclinical to efficacy trials. There is a pressing need to accelerate the pace of medication development for youth AUD by focusing on moving candidate compounds through the drug development pipeline. Human medication screening paradigms can provide an essential bridge to test promising preclinical findings in humans before lengthy large-scale efficacy trials are initiated.

Magnetic resonance imaging (MRI) techniques provide promising non-invasive methods to test neural mechanisms of a candidate medication⁷⁸. Two techniques that are particularly relevant for medication development and are also developmentally-appropriate to use with youth are magnetic resonance spectroscopy (MRS) and functional MRI (fMRI)⁷⁹. **MRS** quantifies metabolites in the brain, including glutamate and GABA levels, which are affected by substance use and are therefore targets for substance use medication development⁷⁹⁻⁸¹. Alcohol alters glutamate neurotransmission⁸², which is related to GABAergic functioning, further supporting the use of MRS to test medications for AUD. **fMRI** localizes and quantifies brain activity, allowing for mechanistic understanding of neural substrates affected by the candidate medication. fMRI cue reactivity tasks activate incentive salience and reward circuitry⁸³, and these cue-related brain activation patterns have been modulated by pharmacological intervention; predicted later relapse; and are associated with alcohol craving⁸⁴. Cue reactivity can also be assessed during an olfactory cue reactivity task (measured via heart rate, skin conductance, and subjective ratings)⁸⁵ to better understand psychophysiological effects of potential medications.

Summary. Adolescence and young adulthood are critical periods of time to intervene with emerging AUD and alcohol-related issues. Pharmacological interventions have the potential to bolster the efficacy of psychosocial treatments for youth AUD; however, they must be tailored to youth rather than extrapolating from the adult literature. CBD is a promising candidate pharmacotherapy for youth AUD due to its safety profile, proposed mechanisms, and signal for reducing alcohol-related behaviors in preclinical and clinical work. The purpose of this application is to conduct a translational pilot study to examine the neural, behavioral, and psychophysiological effects of CBD in youth with AUD for the first time. Effects established through this study could pave the way to a larger-scale clinical trial and, ultimately, improved long-term outcomes for youth suffering from AUD.

INNOVATION

MRS- and fMRI-based biomarkers and lab-based paradigms offer novel translational testing of the neural mechanisms of CBD in humans. A key element in translating candidate medications from preclinical to human trials is evaluation of common neural effects; MRS and fMRI provide low-risk, non-invasive means to safely and reliably assess the effects of CBD on youth with AUD. *In vivo* response to olfactory alcohol cues will help further illuminate CBD's effect on cue reactivity to better understand the potential mechanism of CBD's action.

To our knowledge, there are no published trials examining CBD as a potential treatment for youth with AUD or any other substance use disorder during adolescence or young adulthood, and according to clinicaltrials.gov, no trials are currently underway. This will be the first trial examining CBD as a potential candidate medication for youth with AUD. Due to its reported safety profile and tolerability, CBD is well-suited for a youth-specific pharmacotherapy translational trial in AUD.

APPROACH

Pilot Data/Feasibility

3.0 Intervention to be studied

CBD is a promising candidate pharmacotherapy for youth AUD due to its safety profile, proposed mechanisms, and signal for reducing alcohol-related behaviors in preclinical and clinical work. This double blind crossover trial will compare one dose of acute oral CBD (600 mg^{25-27,29}) and placebo, followed by an approximate 18 day washout to allow for CBD clearance³¹ (terminal half-life 18-32 hours after acute oral dose)⁹³.

Though CBD is often well-tolerated, it can cause side effects, such as dry mouth, diarrhea, reduced appetite, drowsiness, and fatigue. CBD can also interact with other medications that some people take, such as blood thinners. These side effects are usually mild and go away even with continued use of CBD.

"Increased risk of suicidal thoughts or behavior" is a CBD risk per package insert. However, a recently published meta-analysis indicates no risk for increased suicidality with CBD at this dose or over chronic dosing periods (Klein et al., 2021). Consistent with all of our youth substance use medication studies, we carefully assess participant suicidality and manage appropriately in the event of any compromise to safety.

We do not predict severe adverse events from a single 600 mg CBD dose. All participants will be evaluated by the study medical clinician. The DSMB will review adverse events every 6 months. Concurrent medications with potential interactions with CBD are included in the exclusion criteria. Medication response and tolerability/adverse events will be assessed at each visit.

The suggested maximum target daily dosing for children with epilepsy is 25 mg/kg/day; therefore, even for a low-weight adolescent, the proposed single dose is well within target range of tolerability. A previous within-subjects study in adults with autism spectrum disorder used an acute oral dose of CBD (600 mg) and successfully prevented carry-over effects with a 13-day washout period²⁶. Further, a single dose of 600 mg has been shown to modulate brain metabolite levels measured with MRS^{25,26} and blood oxygen level dependent (BOLD) signal measured with fMRI²⁷⁻³⁰ as compared to placebo in clinical populations (autism spectrum disorder, clinical high risk for psychosis, and psychosis) and healthy controls.

Most studies in children, adolescents, or young adults are long-term studies examining the effects of CBD within epilepsy. CBD doses in those studies usually range between 0.5 mg/kg/day to 28.6 mg/kg/day, with 37% reporting drowsiness and 16% reporting fatigue⁹⁴. In adult studies giving an acute dose of 600 mg, there have been either no adverse events⁹⁵⁻⁹⁷ or low rates for sedation or tiredness (e.g., 15%⁹⁸; 22%⁹⁹). There are currently no studies on the effect of oral purified CBD on driving ability, but one study found no differences on driving performance when comparing higher CBD-cannabis flower (smoked) as compared

to placebo at 40 or 240 minutes after use¹⁰⁰. We will carefully evaluate drowsiness and fatigue before participants are able to leave from the facility, and we will arrange safe transportation accordingly.

The metabolism and absorption of CBD can be modulated by food intake, with a 4-to-5 fold increase in bioavailability after a high-fat meal⁷⁴; thus, all participants will eat a standardized high-fat snack with each medication administration. Neuroimaging will be conducted 3 hours after CBD/placebo administration to allow for CBD to reach its peak plasma concentration^{26,101}. PI [name] received an FD exemption for using Epidiolex (CBD) with adolescent substance users (IND161500).

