22. Reasons for Quitting Questionnaire-Cannabis (Steinberg et al., 2005) is a 27-item scale designed to assess common reasons for wanting to quit using cannabis. The scale will be modified to reflect quitting or reducing cannabis use and will only be administered to participants who report an abstinence or reduced use goal for cannabis on the "Thoughts About Abstinence Scale". Note that only items 1-27 will be administered.
23. The Motivation to Quit Measure (Turner & Mermelstein, 2004) is a single item assessing motivation to quit smoking. This has been adapted to additionally assess motivation to quit vaping or e-cigarette use in the current study. These will be administered if past 60-day cigarette or e-cigarette use is endorsed on TLFB, respectively.
24. The Addiction Growth Mindset Questionnaire (Burnette et al., 2019) is a 3-item questionnaire designed to assess whether individuals see their substance use and behaviors as malleable or static in nature.
25. The Modified Fagerström Tolerance Questionnaire (mFTQ; Prokhorov et al., 2000) is a 7-item self-rating questionnaire assessing nicotine dependence in the adolescent population and it will be given to participants that endorse tobacco use in the past 60 days on TLFB.
26. Penn State Electronic Cigarette Dependence Index (Foulds et al., 2015) is a 10-item questionnaire assessing electronic cigarette dependence, given to participants that endorse past 60-day e-cigarette use on TLFB.

Additional Study Specific Assessments

27. Clinical Institute Withdrawal Assessment for Alcohol (CIWA): Alcohol withdrawal will be assessed at the beginning of each session using the CIWA. A score >10 will result in referral to a higher level of clinical care.
28. Columbia Suicide Severity Rating Scale assesses for suicidal ideation at each visit and if a higher level of clinical care is needed.
29. Prior/concomitant medication will assess for eligibility at each medication visit (see exclusion criteria).
30. Adverse events will be assessed after each medication dose.
31. Penetration of the Blind will be assessed after each medication dose to assess the participant's belief about whether they received the placebo or active condition.
32. Cash Choice task is a brief measure of motivation, inhibition, impulsivity.
33. Alcohol Purchase Task (17 items; Murphy et al., 2006) is a behavioral economic measure of motivation for alcohol.

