Alcohol Olfactory Cue Reactivity Task			X	X	
Magnetic Resonance Imaging			X	X	
Estimated Visit Length (hours)	2-3	1-1.5	5	5	0.5

Visits. On the day of the Entryway assessment, we will conduct an additional in-person Screening Visit, to set up and trial daily texting, ensure inclusion/exclusion criteria, and collect additional study-specific information. Visits 1 and 2 will be in-person and include neuroimaging. There will be a brief Visit 3 about two and a half weeks after Visit 2 that will be via phone or video to update the participant's information.

Daily texts. After Visits 1 and 2, participants will receive a daily text for the next 18 days with a maximum of 30 days if necessary due to scheduling. The text will have a link to an on-line REDCap survey that will ask about the prior day's use of alcohol, cannabis, tobacco, CBD, and other substances. The link can also be e-mailed if the participant prefers.

Alcohol cue exposure procedure. Consistent with published procedures utilized with youth at MUSC, all participants will undergo an olfactory alcohol cue exposure procedure⁸⁵ before the neuroimaging session. In a counterbalanced order, participants will smell water, a bottle or can of the participant's preferred alcoholic beverage, and a cup of apple juice (as this is not typically used as a mixer with alcohol¹⁰⁷) for three minutes each, with three minute rest periods in between each liquid. Heart rate, skin conductance, and self-reported craving (via the Alcohol Urges Questionnaire) will be acquired based on previously used protocols¹⁰⁷.

Biological assessments. Combined use of ethanol metabolites and traditional biomarkers [i.e. alcohol breathalyzer, urine ethyl glucuronide (EtG), and blood phosphatidylethanol (PEth)] will be utilized to corroborate self-report alcohol use¹⁰⁸⁻¹¹¹. THC and CBD assays will be collected through urine to corroborate cannabis use. Blood samples will also be used to detect peripheral cytokines. Saliva samples will be collected for profiling of microbial communities via 16S rRNA sequencing. Urine drug tests (comprehensive panel testing for cotinine, cannabinoids, amphetamines, opioids, and benzodiazepines) will be used to monitor other substance use. Urine pregnancy tests will be conducted with participants assigned female at birth. Participants will also be asked to sniff a scented candle and report whether they can smell it and identify the scent, to check basic ability to smell.

Neuroimaging protocol (1 hour).

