Mock scanner: On Visit 1, participants will be introduced to the mock scanner to help them become acclimated to the MR environment and give them the opportunity to practice remaining still while in the magnet, which will minimize motion-related confounds in the imaging data.

Participants will undergo 2 neuroimaging scans (1 scan three hours after CBD, 1 scan three hours after placebo). Breath and urine toxicology samples will be collected before every scan. Saliva samples will be collected before and after every scan. Scans will be performed with a Siemens 3T Prisma^{fit} MRI scanner. Imaging sessions (~60 minutes) consist of:

1. **T1-weighted structural:** A high-resolution anatomical scan will be acquired, to allow subsequent registration to functional images and region-of-interest (ROI) definition.
2. **The Alcohol Cue Reactivity Task:**^{91,92} During the alcohol cue reactivity task, participants are shown pseudorandomly interspersed images of alcoholic (i.e., beer, wine, and hard liquor) and non-alcoholic (e.g., soft drink, juice) beverages, visual control images (i.e., blurred images), and a fixation cross. A magnetic fieldmap will also be acquired to allow geometric unwarping and cost-function masking of EPI images induced by magnetic field inhomogeneities.
3. **Magnetic Resonance Spectroscopy:** The magnetic resonance spectroscopy protocol proposed will be utilizing previously published methods.

Participants will be compensated \$25 for the Screening Visit, \$300 for completing both imaging visits (\$150 V1 and \$150 V2), as well as an additional \$1 per day for submitting their daily text questionnaire for a maximum of 60 days total. Participants will also be eligible for a \$30 referral bonus for everyone they refer who successfully randomizes into this study. Mileage reimbursement will be available to participants who live >25 miles away; the current mileage reimbursement rate, which is updated each year by the state, will be offered.

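### No symptom question is scheduled between discharge on a dosing day and the next visit, and after the second dose the study timetable has no later adverse event assessment

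*Combined protocol and SAP*

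**What the plan says.** All references are to the combined protocol and SAP.

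- **On-site check.** Section 3.0 includes drowsiness and fatigue among the side effects of CBD and notes that oral purified CBD has not been studied for driving. Its safeguard is: "We will carefully evaluate drowsiness and fatigue before participants are able to leave from the facility". Transport home is organised on the basis of that check.
- **Timing.** Section 3.0: "Neuroimaging will be conducted 3 hours after CBD/placebo administration to allow for CBD to reach its peak plasma concentration". Section 10.0: "Imaging sessions (~60 minutes) consist of" the listed sequences. Table 1 estimates 5 h for Visit 1 and 5 h for Visit 2. Section 3.0 gives a "terminal half-life 18-32 hours after acute oral dose".
- **Daily survey.** Section 10.0 says of the period following each dosing visit: "participants will receive a daily text for the next 18 days with a maximum of 30 days if necessary due to scheduling". Its listed content is the previous day's alcohol, cannabis, tobacco, CBD and other substances. No symptom item is listed.
- **AE assessment.** Sections 3.0 and 10.0 say that AEs are assessed at every visit. Item 30 of the measures list in section 10.0 says "Adverse events will be assessed after each medication dose", with no time point or look-back. Table 1 marks AEs at the Study Screener, Visit 1 and Visit 2. The Visit 3 cell is blank, and the clinician meeting there is optional.
- **Visit 3.** Section 10.0 describes a short remote contact about two and a half weeks after Visit 2, held to update the participant's information.

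**The concern.** The protocol picks out drowsiness and fatigue for attention, yet its scheduled enquiry about them ends when the participant leaves the building and resumes only at the next visit, if then. It already contacts every participant daily in that interval, but about something else.

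Two things are at stake. The first is ascertainment: drowsiness on the evening of dosing or the next morning is poorly recovered by a question asked weeks later, so the tolerability record offered in support of a larger trial would be thin. The second is comparability: the first and second doses are followed up differently, so within a participant the two conditions are not observed on the same footing.

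**Working it through.** The plan states no figure on this point to reproduce. The check is clock arithmetic, a reading of the timetable, and the cited event rates.

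**1. When participants leave.** Inputs: visit length 5 h (Table 1), stated peak and scan start 3 h after dosing (section 3.0), scan about 1 h (section 10.0). Pre-dose time is not stated; I assume 0 to 1 h.
- Discharge after dosing = 5 − pre-dose time = 5 − 1 to 5 − 0 = 4 to 5 h.
- Discharge after stated peak = 4 − 3 to 5 − 3 = 1 to 2 h.
- Scan end = 3 + 1 = 4 h after dosing, so the lower bound is consistent with leaving directly after the scan.

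**2. Whether exposure continues after discharge.** Fraction of peak remaining = 0.5^(t / half-life), with half-life 18 h and 32 h:
- 2 h after peak: 0.5^(2/18) = 0.926 and 0.5^(2/32) = 0.958, or 93 to 96%.
- 24 h after dosing, which is 21 h after peak: 0.5^(21/18) = 0.445 and 0.5^(21/32) = 0.635, or about 45 to 63%.

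These are upper bounds, because concentrations fall faster in early distribution than at the terminal rate. They show only that exposure may extend past discharge, not that sedation does.

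**3. What is scheduled after each dose.**

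| | First dose (Visit 1) | Second dose (Visit 2) |
|---|---|---|
| Before leaving | Drowsiness and fatigue evaluated | Same |
| Daily survey | Substance use only | Substance use only |
| Next AE assessment in Table 1 | Visit 2, about 18 days later, by recall, no look-back written | None; Visit 3 cell blank |

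Order is counterbalanced, so about 50 × 0.5 = 25 participants receive CBD as the second dose.

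**4. How many participants are affected.** For acute 600 mg doses in adults, section 3.0 cites studies with no adverse events and studies with 15% or 22% sedation or tiredness. With 50 CBD doses: 50 × 0 = 0, 50 × 0.15 = 7.5, 50 × 0.22 = 11. For the 25 who receive CBD second: 25 × 0 = 0 to 25 × 0.22 = 5.5. These are all expected cases, including any seen on site. The documents give no basis for estimating the number missed.

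**5. Effect on the CBD–placebo comparison.** Let rC and rP be the true rates of drowsiness starting at home, and d1 and d2 the probabilities that a scheduled question picks it up after the first and second dose. Assume equal numbers in each order and detection that depends only on period. The expected recorded rates are rC(d1 + d2)/2 and rP(d1 + d2)/2, so the recorded difference is (rC − rP)(d1 + d2)/2. On the timetable as drawn, d2 = 0, and the multiplier cannot exceed 1/2 even with perfect recall at Visit 2 (d1 = 1). The difference shrinks, but neither condition is favoured on average.

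**The case against.** The strongest reply is that follow-up does not stop at the door. AEs are to be assessed at every visit and after each dose. Visit 2 carries an AE assessment that can pick up drowsiness after the first dose. Section 15.0 gives participants and parents access to a clinician at any hour for emergencies and describes serial AE monitoring by the clinician. Section 8.0 describes active contact between visits, and section 13.0 has AEs reviewed weekly. Participants are on site through the stated peak. Section 3.0 calls the side effects usually mild, and no endpoint in section 4.0 is a tolerability measure.

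Much of this stands, and it limits the point. A reader might infer that drowsiness after discharge is never asked about. The documents do not support that for the first dose, because Visit 2 has an AE assessment. A reader might also infer that the half-life contradicts the pre-departure check, or that it predicts sedation at home. The check and the half-life are compatible, and nothing in the protocol links concentration to sedation. The figure "with 37% reporting drowsiness and 16% reporting fatigue" should not be applied here either: section 3.0 attributes it to long-term use in epilepsy, not to a single dose.

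These safeguards do not supply the missing question. Emergency access depends on the participant calling and is unlikely to yield reports of ordinary drowsiness. Contact between visits is described as a retention measure. Weekly review can only examine events that have been reported. The promise to assess at every visit would cover Visit 3, but Table 1 says otherwise.

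**Conclusion.** The point holds as a gap in data collection together with one inconsistency in the schedule. No symptom question is scheduled between discharge and the next visit. Capture after the first dose rests on recall at about 18 days. After the second dose, which is CBD for about 25 of 50 participants, Table 1 has no later AE assessment, in conflict with the text of sections 3.0 and 10.0.

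The cited acute rates put the total at about 0 to 11 of 50 participants with sedation or tiredness after CBD, on site or at home; how many would be missed is unknown. The discharge time of 4 to 5 h rests on the assumed 0 to 1 h of pre-dose procedures, and the 25 rests on equal allocation to the two orders with all 50 dosed twice.

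A reader might infer that the unequal follow-up biases the CBD–placebo contrast in favour of one condition. Counterbalancing argues against that: each condition comes second about equally often. The likely consequence is under-counting in both conditions and a diluted difference. The primary neural and psychophysiological endpoints are not affected. This is a modest weakness that is cheap to repair.

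**What to change.** Add two short items to the existing daily REDCap survey in the days after Visits 1 and 2: one on drowsiness or fatigue, and one asking about any other new symptom. Use the same wording and the same number of days after both doses, and enter positive answers in the AE log with their onset date so that each event can be assigned to a dose. The survey's previous-day window already reaches back to the dosing evening. The response to a reported symptom remains with the study's clinicians under the existing AE procedures.

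Separately, reconcile the statements that AEs are assessed at every visit (sections 3.0 and 10.0) and after each dose (item 30, section 10.0) with the blank Visit 3 AE cell in Table 1, and state the look-back period for the AE question at each visit.

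The survey is already sent daily and paid at $1 per day, so the cost is two items, a slightly longer text and some added AE review.
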